9.3 Reference Safety Information

The approved Reference Safety Information (RSI) is:

- Section 4.8 of the Uvadex 20 micrograms/ml Solution Summary of Product Characteristics (SmPC) dated 25/08/2021.

The SmPC is available via MHRA website: <https://products.mhra.gov.uk/>

9.4 Recording and Reporting SUSARs

All SARs or suspected SARs that occur during this trial must be reported by site to NCTU immediately (and no later than 24 hours of the site becoming aware of the event), through the provided SAE reporting method (see section 9.2). This will automatically be distributed to the Sponsor and CI.

The assessment of expectedness will be performed by the CI on behalf of Sponsor. Where the CI is unavailable, another medically qualified individual may be delegated this task via the trial delegation log. The assessment of expectedness will be performed against the approved RSI for the trial.

The RSI is contained within the Uvadex SmPC section 4.8 (see section 9.3 above)

All SUSARs must be reported to the MHRA and REC. Reporting to MHRA and REC will be performed by the trial Sponsor. This is reported using the electronic SUSAR form via the eSUSAR website. A copy of the electronic form and the CTIMP safety report will be sent to the REC in line with sponsor standard operating procedures.

Fatal and life-threatening SUSARs must be reported to the MHRA within 7 calendar days of notification (with a further 8 days for follow up information) by the Sponsor.

Non-life-threatening SUSARs must be reported to the MHRA by the Sponsor no later than 15 calendar days after notification with any relevant follow-up information sought and reported as soon as possible after the initial report.

NCTU will be responsible for ensuring that the CI undertakes the expectedness assessment to determine if a SAR is unexpected and requires reporting as a SUSAR. The reporting timeframe starts at day zero when the Sponsor is in receipt of a minimum set of information:

- Sponsor trial reference and trial name (sponsor reference).
- EudraCT number.
- Patient trial number
- Name of IMP(s).
- Date of notification of the event.
- Medical description of the event.
- Date of the onset of the event (including time of onset if available and event end date if applicable)
- Causality assessment.
- Seriousness of the event, particularly if life threatening or fatal.
- An identifiable reporter (e.g. PI).

The site is expected to fully cooperate with the NCTU in order that a full and detailed report can be submitted to the MHRA and REC within the required timelines.

Site PIs will be informed of all SUSARs by NCTU.

9.5 Protocol Specific Reporting Exclusions

Pre-planned hospitalisations (e.g. elective surgery) or scheduled treatment for pre-existing conditions that are not associated with clinical deterioration do not need to be reported as SAEs. Hospitalisations for administration of trial ECP therapy only will not be considered as SAEs.

9.6 Responsibilities

Principal Investigator or delegate

- Checking for AEs and ARs when participants attend for treatment or follow-up
- Using medical judgement in assigning seriousness and causality on events
- Ensuring that all SAEs and SARs, are recorded and reported to the Sponsor within 24 hours of becoming aware of the event and provide further follow-up information as soon as available.
- Ensuring that AEs and ARs are recorded and reported to the Sponsor in line with the requirements of the protocol.

Chief Investigator

- Clinical oversight of the safety of trial participants, including an ongoing review of the risk/benefit.
- Using medical judgement in assigning seriousness, causality and expectedness of SAEs where it has not been possible to obtain local medical assessment.
- Using medical judgement in assigning expectedness to SARs in line with the RSI.
- Immediate review of all SUSARs.
- Review of specific SAEs and SARs in accordance with the trial risk assessment and protocol.
- Review/assignment of Medical Dictionary for Regulatory Activities (MedDRA) preferred terms System Organ Class coding for all SAEs and SARs.
- Confirming what changes to RSI are required as part of the annual review process of the SmPC.
- Preparing the clinical sections and final sign off of the Development Safety Update Report (DSUR).

Sponsor

- Data collection and verification of AEs, ARs, SAEs, SARs and SUSARs onto a database (may be delegated to NCTU, according to the delegation agreement).
- Reporting safety information to the independent oversight committees for the ongoing assessment of the risk/benefit ratio throughout the life of the trial (may be delegated to NCTU).
- Assessment of expectedness of any SUSARs (delegated to the CI)
- Expedited reporting of SUSARs to the Competent Authority (CA) and REC within required timelines
- Notification of all investigator sites of any SUSAR that occurs (may be delegated to NCTU).
- Reviewing RSI at least annually and notification of PIs of any required updates (may be delegated to NCTU)
- Preparing tables and other relevant information for the DSUR in collaboration with the CI and ensuring timely submission to the MHRA and REC (may be delegated to NCTU)

TSC/DMC/TOC

- Review of safety data collected to date to identify any trends

9.7 Notification of Deaths

Fatal SUSARs will be reported within 7 days to REC and MHRA. Monitoring of all other deaths will occur via the TMG, IDMEC and the TSC.

All Participant deaths will need to be reported as SAEs, with the reason for death identified on the SAE form and recorded in the eCRF. The only exception to this is death due to progression of CLAD which will be reported in the eCRF, but not as an SAE.

9.8 Pregnancy Reporting

In the event of a study participant or the partner of a study participant becoming pregnant on the trial the site must notify NCTU within 24 hours of becoming aware of the pregnancy and complete a pregnancy reporting form. The pregnancy reporting form should be sent to [contact].

Site must approach the trial participant or the partner of a trial participant to obtain consent to follow to outcome of pregnancy. For the female partner of a male trial participant, an E-CLAD UK Partner Pregnancy Information Sheet will be provided.

In the event that a congenital anomaly or birth defect does occur, this must be reported as a SAE.

9.9 Overdose

Where an occurrence of methoxsalen over-dosing is discovered, this should be notified to the PI immediately and any appropriate care or guidance given to the patient. In the event of methoxsalen overdose, the patient should be kept in a darkened room for at least 24 hours.

An overdose, whether intentional or accidental must also be reported immediately to NCTU (email: [contact]). Whilst it is not in itself an adverse event or serious adverse event, any untoward medical occurrence as a result of an overdose, or any condition that leads to an overdose being taken is considered an AE or SAE and should be reported as per section 9.2. Details of the event must be recorded in the case report form for the trial and the participant's medical records.

9.10 Reporting Urgent Safety Measures

An Urgent Safety Measure (USM) is an action that the Sponsor or an Investigator may take in order to protect the subjects of a trial against any immediate hazard to their health or safety. Upon implementation of an USM by an Investigator, the Sponsor, CI and NCTU must be notified immediately and details of the USM given. The Sponsor must inform the MHRA and the NHS REC within 3 days of the USM taking place in accordance with the Sponsor's standard operating procedures. The MHRA may alert the trial team to a new safety signal identified for the trial IMP. In the event of this occurring, the IMP may need to be discontinued with immediate effect and a temporary halt submitted to the competent authorities. The sponsor is required to put the trial on hold with immediate effect.

9.11 Development Safety Update Reports

The following reports will be submitted each year as a condition of the authorisation to undertake a clinical trial or as a condition of a favourable opinion from a REC.

In the UK, a DSUR will be submitted to the MHRA and NHS REC once a year on the date of CTA approval of the trial. NCTU must ensure that the report is submitted within 60 days of the end of the reporting

period. The Trial Management Group must contribute to the compilation of the DSUR with the CI being involved in completion of the relevant sections requiring medical input and assessment of any newly identified risks and the summary of benefit-risk considerations. The CI must review and authorise the final report before it is ready for submission. The DSUR should also be reviewed by the NCTU QA Manager and Sponsor Representative prior to submission. NCTU staff will prepare and submit DSURs for the trial, in accordance with NCTU SOPs.

An NRES CTIMP Safety Report Form will be sent to REC along with the DSUR. Reports of SUSARs in the UK, urgent safety measures and any other safety reports submitted, for example, reports of a data monitoring committee, will also be accompanied by a Safety Report Form.

A NRES Annual Progress Report for CTIMPs will be prepared and submitted by the CI to REC, and copied to Sponsor, on the anniversary date of the REC favourable opinion.

10. STATISTICAL CONSIDERATIONS

The statistical analyses are described in full detail in a separate Statistical Analysis Plan. Statistical analysis will take place after data lock.

10.1 Sample Size Calculation

Our proposed sample size is 90 patients. We used published evidence to underpin our sample size calculations. Todd et al reported changes in longitudinal lung function in 213 CLAD patients who did not receive ECP; 27% had a <10% loss in FEV1 within 6 months, equating to stabilisation. We assume conservatively that in the SOC arm, 30% patients will be responders. The three largest ECP in CLAD studies show 54-61% patients had <10% decline in FEV1 within 6 months; we therefore assume a 55% stabilisation rate in the ECP arm. With 90 patients randomised 1:1 between SOC and ECP arms, we would have 80% power (5% one-sided type I error rate) to detect a difference when the ECP arm has a 55% response rate and the SOC arm a 30% response rate. This calculation assumes Barnard's exact test is used in the analysis.

As the primary endpoint is a composite responder endpoint, our primary analysis will utilise the augmented binary method to test the difference in response rate as the primary analysis (see Section 10.10.2). Previous work has shown that the augmented binary method increases the power of the analysis equivalent to increasing the sample size by at least 35% without any inflation in the type 1 error-rate. Even allowing for 10% of patients dropping out, we are thus confident power will be above 85% for this analysis, and believe it is likely to be above 90%. Conservatively, for the augmented binary analysis we believe the maximum number of patients required to achieve 80% power is 68.

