1.2 Rationale

A systematic review using full text search terms for [ECP] + [lung transplantation] or [CLAD] or [BOS] or [RAS] in PubMed yielded 5 reviews, 2 mechanistic studies and 9 relevant clinical studies. These studies used ECP in lung transplant recipients with CLAD and showed promise in slowing or halting its progression (11). However, these are universally single centre retrospective studies conducted over prolonged periods of time while other aspects of care were also evolving. There was a lack of proper untreated controls and ECP was offered to only selected patients with CLAD. None of these studies were performed in the UK in an NHS setting, so high-quality evidence of the efficacy of ECP in CLAD treatment has not yet been established. The proof of concept for use of ECP in CLAD comes from 4 larger studies (described below) that represent a collective experience of 223 lung transplant recipients with CLAD, including RAS and BOS phenotypes. Of the 4 studies, 3 reported a clinical response ranging from 54–61%. None were conducted as a prospective randomised controlled trial (RCT) and all have limitations of bias in patient selection.

Morrell et al (12) reported retrospective outcomes on 60 patients treated with ECP for progressive BOS. They compared rate of decline in FEV1 for 6 months before and after commencement of ECP showing a significant reduction in the rate from -116 mls/month to -28.9 mls/month ($p=0.0001$). 25% of treated patients showed an increase in lung function within 6 months. There was a 13% rate of hospitalisation for line sepsis, including 1 death, but this was limited to only those with long-term indwelling apheresis catheters; no line infections were reported in those treated through peripheral cannulation. There was no control group and selection of patients for treatment implied bias.

Jaksch et al (13) reported a single centre experience of treating 51 BOS patients with ECP. 61% of those treated demonstrated improvement or stabilisation in FEV1 defined as <5% decline over the first 6 months of treatment. ECP treatment response was also associated with an improved survival and reduced need for retransplantation compared to patients with BOS not getting ECP and those not responding to ECP. There was a selection bias as only 26.2% of BOS patients at this centre received ECP. No adverse events (AEs), including serious infections, were reported.

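### Protocol section 10.1 states 80% power for Barnard's test on 90 patients where exact calculation gives about 77%; the figure of 68 has no dropout allowance, and the response rates are for FEV1 alone

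*Protocol*

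**What the plan says.** All the design inputs are in Protocol section 10.1.

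- Size and allocation: "Our proposed sample size is 90 patients", and "With 90 patients randomised 1:1 between SOC and ECP arms".
- Error rate, power and ECP response: "we would have 80% power (5% one-sided type I error rate) to detect a difference when the ECP arm has a 55% response rate"; SOC response is set at 30%.
- Test behind the figure: "This calculation assumes Barnard's exact test is used in the analysis".
- The primary analysis is then named as the augmented binary method and credited with a gain worth at least 35% more patients. Power is put above 85% even with 10% dropout, and for this analysis "the maximum number of patients required to achieve 80% power is 68".
- Sources of the rates: 27% of 213 patients without ECP lost less than 10% of FEV1 within 6 months, rounded up to 30% for SOC. For ECP, "The three largest ECP in CLAD studies show 54-61% patients had <10% decline in FEV1 within 6 months", taken as 55%.

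The primary endpoint (sections 2.1, 7.3 and 10.3.1) is stricter than any of these source outcomes. It requires at most a 10% loss in both FEV1 and FVC at 24 weeks, and no fall above 20% in either by week 12.

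**The concern.** A power statement that names the test, the rates, the error rate and the sample size can be checked exactly, and this one does not reproduce. The later figures in section 10.1 are built on it, so they are worth checking too. The figure of 68 is offered as a conservative maximum but appears to be a number of evaluable patients, placed straight after a sentence about dropout. The response rates describe a different, easier outcome than the one to be tested. At stake is whether a reader can rely on section 10.1 as an account of the power the trial has.

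**Working it through.** **1. Power of the named test.** Inputs (section 10.1): 45 v 45, rates 0.30 and 0.55, one-sided 5%. Method: list all 46 x 46 outcome tables, order them by the test statistic, take the largest rejection region whose maximum size over the common response rate is at most 5%, and sum the binomial probabilities of that region at 0.30 and 0.55.

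| Test, 45 v 45 | Maximum size | Power |
|---|---|---|
| Barnard, pooled score (critical z 1.707) | 4.85% | 76.9% |
| Barnard, unpooled score; Boschloo | 4.85% | 76.9% |
| Barnard, original CSM ordering | 4.92% | 77.8% |
| Uncorrected z-test (critical z 1.645) | 5.94% | 79.7% |

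With the pooled score, Barnard's test gives 79.2% at 49 per arm and 80.3% at 50 per arm, so about 100 patients are needed.

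The stated 80% can be recovered without an exact test. With d = 0.25, n = 45 and s = √(0.30 x 0.70 + 0.55 x 0.45) = √0.4575 = 0.676, the unpooled normal approximation is Φ(d√n/s − 1.645) = Φ(2.479 − 1.645) = Φ(0.835) = 79.8%. With the pooled variance under the null it is 78.2%.

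**2. The figure of 68.** 90/1.35 = 66.7, and 68 x 1.35 = 91.8, so 68 patients with the full 35% gain are worth about the original 90. At 91.8 effective patients (about 46 per arm), power is 77.8% by Barnard's test, 78.9% by the pooled normal approximation and 80.5% by the unpooled one. So 68 is consistent with 80% on the unpooled scale, but only if all 68 are evaluable.

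With 10% lost, 68 x 0.9 x 1.35 = 82.6 effective patients. Power is then 75.0% (pooled) or 76.8% (unpooled) by normal approximation, and 72-74% by Barnard's test at 41 v 42 and 41 v 41. Keeping 68 evaluable requires 68/0.9 = 75.6, that is 76 recruited.

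**3. The claim of more than 85%.** 90 x 0.9 x 1.35 = 109.4 effective patients. Barnard's test gives 82.9% at 54 (SOC) v 55 (ECP), 83.9% at 54 v 54 and 85.0% at 55 v 55; the spread is discreteness. Normal approximation gives 84.9% (pooled) and 86.2% (unpooled). The range is about 83-86%.

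**4. Rates for the stricter endpoint.** The protocol gives no composite response rates, so those below are assumptions. Barnard's test, 45 v 45:

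| ECP v SOC (assumed) | Difference | Power |
|---|---|---|
| 50% v 25% | 25 points | 79.5% |
| 49.5% v 27% (both stated rates x 0.9) | 22.5 points | 71.2% |
| 44% v 24% (both stated rates x 0.8) | 20 points | 63.6% |

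Added conditions can only lower each arm's rate at a given FEV1 threshold. Power falls materially only if the absolute difference shrinks.

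**5. Description of the sources.** Section 1.2 gives four studies of 64, 60, 51 and 48 patients. The 54%, 61% and 60% results come from those of 64, 51 and 48. The 60-patient study, second in size, reports no such rate, so the three are not the three largest. Section 1.2 also says that "61% of those treated demonstrated improvement or stabilisation in FEV1 defined as <5% decline over the first 6 months of treatment", which is not the <10% threshold given in section 10.1.

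**The case against.** The strongest reply is that Barnard's test is only a benchmark. The primary analysis is the augmented binary method and the first sensitivity analysis is logistic regression (section 10.3.1), so a 2 to 3 point error need not carry over. That stands, and it limits the importance of the point; it does not make the stated figure right for the test named.

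A reader might go further in four ways that the protocol does not support.

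- *That 68 should become 74 evaluable or 83 recruited* (100/1.35 = 74.1; 74.1/0.9 = 82.3). This applies the 35% gain to Barnard's corrected size, but section 10.1 does not say against which analysis the gain was measured, and it says at least 35%. The number would be higher than 76 on that reading, but the protocol does not establish it.
- *That 68 is meant to excuse recruiting fewer than 90.* No section gives it that role, and section 10.3.6 plans no formal interim analysis.
- *That the stricter endpoint certainly costs power.* The effect depends on the unknown difference. The protocol also keeps some margin: SOC is raised from 27% to 30%, and 55% lies near the bottom of 54-61%.
- *That the source slips inflate the ECP rate.* A <5% decline is the stricter definition, so that study's rate for <10% would be at least 61%. No input changes.

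The dropout arithmetic treats lost patients as contributing nothing. Section 5.5.3 counts identified non-responders as non-stabilised, section 10.2 analyses everyone recruited, and the joint model uses week 12 as well as week 24, so some dropouts would still inform the analysis. The 76 is therefore a cautious figure.

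**Conclusion.** The point holds. On the protocol's own inputs, Barnard's test has about 77% power with 90 evaluable patients (76.9% to 77.8% by ordering), not 80%; this rests on no outside assumption. A z-test or normal-approximation figure attributed to Barnard's test is the likely explanation, though the protocol does not show the derivation. The 68 leaves nothing for the 10% dropout and corresponds to about 76 recruited on the protocol's own scale, assuming complete loss of dropouts. The claim of more than 85% is borderline rather than refuted, at about 83-86%, and takes the 35% gain as given. The mismatch between FEV1-only rates and the composite endpoint is a fact; the 64% to 80% range is illustrative and rests on assumed rates. None of this shows that the primary analysis is underpowered or that 90 is the wrong number to enrol.

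**What to change.** Reword section 10.1, leaving 90 enrolled:

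- Restate the power of Barnard's test as about 77% on 90 evaluable patients.
- Label 68 as evaluable, give the recruited number with 10% dropout (about 76), and state the reference analysis for the 35% gain.
- Describe the claim of more than 85% as about 83-86%.
- Add power over a stated range of composite response rates, for example 44-55% v 24-30%, noting that the source rates are for FEV1 alone.
- Correct the source description: the 61% result used <5% decline, and the three studies are not the three largest.

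The cost is a wording change and slightly less favourable stated figures. Design, enrolment and analysis are unaffected.

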10.2 Analysis Populations

All primary analyses of the primary and secondary outcome efficacy analyses will be carried out on an intention to treat basis in the full analysis population. The full analysis population will contain all patients recruited into the study (regardless of whether they were later found to be ineligible, allocated to the incorrect treatment, in violation of the protocol, etc.)

Safety analyses will be carried out similarly, in a safety population consisting of all patients recruited into the study.

Secondary efficacy analyses will be carried out in a per-protocol analysis population. The per-protocol analysis population will consist of the patients who completed a full-course of the treatment they were originally assigned (i.e. 12 weeks of treatment for the ECP plus SOC arm), as per the protocol.

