5.12.2. Investigator Led Withdrawal from the trial

The investigator/treating clinician may withdraw a participant from the trial at any time if they deem it necessary for the following reasons:

- Continuing to attend trial visits and undergoing trial assessments would place unreasonable demands on the physical or psychological health of the participant. If participant and investigator agree, any assessments occurring as part of routine care would also be recorded in the eCRF.

- The participant loses capacity for a prolonged period.
- An adverse event, which results in inability to continue to comply with trial procedures.
- Inability to secure appropriate vascular access for ECP treatment to be delivered to participant in the ECP+SOC arm.
- Pregnancy.
- Significant protocol deviation or non-compliance.
- Termination of the clinical trial by the Sponsor.

Where the decision is taken by the clinician to fully withdraw the participant from the trial, the following procedures will apply:

- If the participant has not yet received any ECP treatment, the participant should not participate in any further trial-related procedures.
- If the participant has received any ECP treatment including IMP administration as part of the process, the ECP treatment should be stopped, and followed up for adverse event reporting purposes only for an additional 4 weeks.

Information that a participant has received ECP treatment even if incorrectly enrolled/randomised must be documented in the eCRF.

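### Section 10.2 analyses safety only by assigned arm in all recruited patients, so ECP-related event rates are understated to the extent that ECP-arm participants never start

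*Protocol*

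**What the plan says.** Protocol section 10.2 first deals with efficacy, whose primary analyses "will be carried out on an intention to treat basis in the full analysis population". That population keeps every recruited patient "regardless of whether they were later found to be ineligible, allocated to the incorrect treatment, in violation of the protocol, etc". The next paragraph turns to safety: "Safety analyses will be carried out similarly, in a safety population consisting of all patients recruited into the study". The only other population in the section is the per-protocol one, and it is reserved for secondary efficacy analyses. Nothing in 10.2 requires at least one ECP treatment for a safety analysis or groups safety by treatment received.

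Section 5.12.2 foresees ECP-arm participants who are never treated. One listed reason for withdrawal by the investigator is "Inability to secure appropriate vascular access for ECP treatment to be delivered to participant in the ECP+SOC arm". For a participant withdrawn before exposure it says: "If the participant has not yet received any ECP treatment, the participant should not participate in any further trial-related procedures". The additional four weeks of adverse-event follow-up in that section is given only for those who have received ECP.

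**The concern.** ECP is an invasive procedure combined with an investigational product, so readers of the safety results will want to know how often harm occurs in people who had it. An arm-level rate over everyone assigned answers a different question: how often harm occurs under a policy of offering ECP. If some of the ECP arm never start, they add to the denominator but can contribute no event that depends on treatment, such as a reaction to methoxsalen or photosensitivity.

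The follow-up rule adds to this. A participant withdrawn by the investigator before any ECP can sit in the denominator with little adverse-event follow-up, which tends to lower the ECP arm's count of events of any kind. With about 45 participants per arm, the safety estimates are already imprecise, and an avoidable downward shift does not help.

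**Working it through.** The protocol states no safety rate and no expected number untreated, so there is no figure of its own to reproduce. The check is of how the stated rule behaves.

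**Inputs**
- Arm size: section 10.1 states "Our proposed sample size is 90 patients", randomised 1:1, so 90/2 = 45 per arm if the split is exact.
- u, the number in the ECP arm never treated: not given. Assumed 1, 2, 3 and 5.
- True event rate among the treated: 13%, borrowed from section 1.2, where a retrospective cohort of 60 ECP-treated BOS patients had that rate of hospitalisation for line sepsis. It is used only to size the effect and is not a forecast for this trial.

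**Step 1: can u be above zero?** Three routes appear in the protocol.
- Failed vascular access (5.12.2), which arises only in the ECP arm.
- A contraindication on baseline safety bloods. Section 5.2.2 says they may reveal one, 5.3.2 asks for randomisation during the baseline visit, and 5.12.3 provides for replacement when bloods show ineligibility. Section 5.3 also says participants are confirmed eligible before randomisation, so this route depends on when results return.
- Withdrawal before the next visit after baseline (5.12.3).

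Anyone randomised before dropping out by one of these routes remains in the all-recruited population of 10.2.

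**Step 2: dilution.** For an event that only treated participants can have:

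reported rate = true rate × (45 − u)/45; relative understatement = u/45.

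| u (assumed) | Reported rate if true rate is 13% | Relative understatement |
|---|---|---|
| 1 | 0.13 × 44/45 = 12.7% | 2.2% |
| 2 | 0.13 × 43/45 = 12.4% | 4.4% |
| 3 | 0.13 × 42/45 = 12.1% | 6.7% |
| 5 | 0.13 × 40/45 = 11.6% | 11.1% |

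**Step 3: replacement.** Replacing non-starters under 5.12.3 does not remove the dilution, because those replaced were still recruited. If all five were replaced in the same arm, the factor would be 45/(45 + 5) = 0.90, an understatement of 10% instead of 11.1%.

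**Step 4: events not seen at all.** With zero events in n participants, the one-sided 95% upper bound is 1 − 0.05^(1/n). On 45 this is 6.4%; on 40 treated (u = 5) it is 7.2%. The as-randomised denominator makes the excluded risk look slightly lower than the treated experience supports.

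**Step 5: scale against sampling error.** The standard error of a 13% rate on 45 is √(0.13 × 0.87/45) = 5.0 percentage points. The shift at u = 5 is 13.0 − 11.6 = 1.4 points.

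**Step 6: after the change.** With treated participants as the denominator, a true 13% rate has an expected reported value of 13.0% whatever u is.

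**The case against.** The strongest reply is that the as-randomised analysis is the right one for the stated aim. Section 2.2 asks how two treatment strategies affect outcomes and lists adverse events from randomisation to 24 weeks; 9.2 records them in both arms from consent. A comparison of strategies calls for assigned groups. This stands, and it is why the as-randomised table should be kept.

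Second, participants who never start are not free of ECP-related harm. A central line may be placed before the first cycle (5.2.4, 8.2.3), and 9.2 lists failure to obtain access among causes of unscheduled hospitalisation reportable as serious events. A plain split into at least one ECP treatment against none would move such harm into the comparator group. This also stands: the factor in the working applies only to events that need treatment, and the added table must be built to avoid that shift.

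Third, the numbers untreated should be low. Inadequate access is an exclusion criterion (4.2) and access is assessed at baseline (5.2.4). A participant who merely stops allocated treatment can remain in follow-up (5.11), and those withdrawn are asked to allow use of routine data (5.12). These points limit the size but do not bring it to zero.

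A reader might infer two further things that the documents do not support. One is that the gap of up to 28 days before the first cycle (8.2) is itself a source of untreated participants; it is a delay to starting, and only a window in which someone might drop out. The other is that ECP harms will leak into the SOC column. SOC in the trial excludes ECP (8.1) and rescue treatment requires withdrawal first (5.5, 5.5.3), so no ordinary route is described. At an assumed 13% risk, one such case would add 0.13/45 = 0.3 percentage points to the SOC rate.

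Finally, the SAP is not among the documents at hand and may already contain an exposure table. The point is confined to what 10.2 itself fixes.

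**Conclusion.** The point holds as a minor one. Section 10.2 states a rule for safety, and under that rule rates of events that require ECP treatment are understated by u/45. The relative understatement is 2% at u = 1 and 11% at u = 5, which is well inside sampling error for any single rate. Both u and the 13% rate are assumptions, and 45 per arm assumes an even split. Reading the rule as analysis by assigned arm rests on the word *similarly* following the intention-to-treat sentence; that is the natural reading and nothing in the protocol contradicts it.

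A reader might go further and conclude that as-randomised safety analysis is wrong here, or that it errs towards reassurance for every kind of event. Neither follows. The assigned-arm comparison answers the question in 2.2, and for harm from line placement or failed access before a first treatment it is the treated-only set that would lose events.

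**What to change.** Keep the as-randomised adverse-event comparison and add to section 10.2 a co-reported safety table by treatment actually received, specified as follows.
- The ECP denominator is participants who received at least one ECP treatment.
- Harms from line placement or attempted access before a first ECP treatment stay under ECP and are never moved to the SOC group. Where the participant never went on to treatment, show them on a separate line so that numerator and denominator match.
- Any SOC participant given ECP is shown under ECP.
- The number in the ECP arm never treated is reported, with reasons, so that u is visible.

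No new data are needed to identify who was treated: 5.12.2 requires receipt of ECP to be documented even after incorrect enrolment or randomisation, and dose and compliance are recorded under 8.4 and 8.9. The cost is a wording change in the protocol, matching text in the SAP and one extra table. The downside is that the groups in that table are not strictly the randomised ones, so it should be read as a description of harm in those exposed, beside the randomised comparison.
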